17.8.1 Incomplete Start Date

The following rules will be applied to impute the missing numeric fields for an incomplete prior or concomitant medication start date. If the stop date is complete (or imputed) and the imputed start date is after the stop date, the start date will be imputed using the stop date.

Missing month and day

- If the year of the incomplete start date is the same as the year of the first study treatment, the month and day of the first study treatment will be assigned to the missing fields
- If the year of the incomplete start date is before the year of the first study treatment, *December 31* will be assigned to the missing fields
- If the year of the incomplete start date is after the year of the first study treatment, *January 1* will be assigned to the missing fields

Missing month only

- If only the month is missing, the day will be treated as missing and both the month and the day will be replaced according to the above procedure

Missing day only

- If the month and year of the incomplete start date are the same as the month and year of the first study treatment, the day of the first study treatment will be assigned to the missing day
- If the year of the incomplete start date is before the year of the first study treatment, or if both years are the same but the month of the incomplete start date is before the month of the first study treatment, the last day of the month will be assigned to the missing day
- If either the year of the incomplete start date is after the year of the first study treatment, or if both years are the same but the month of the incomplete start date is after the month of the first study treatment, the first day of the month will be assigned to the missing day

17.8.2 Incomplete Stop Date

The following rules will be applied to impute the missing numeric fields for an incomplete prior or concomitant medication stop date. If the date of the last study treatment is missing, impute it as described in Section 16.4. If the imputed stop date is before the start date (imputed or non-imputed start date), the imputed stop date will be equal to the start date.

Missing month and day

- If the year of the incomplete stop date is the same as the year of the last study treatment, the month and day of the last study treatment will be assigned to the missing fields
- If the year of the incomplete stop date is before the year of the last study treatment, *December 31* will be assigned to the missing fields
- If the year of the incomplete stop date is after the year of the last study treatment, *January 1* will be assigned to the missing fields

Missing month only

- If only the month is missing, the day will be treated as missing and both the month and the day will be replaced according to the above procedure

Missing day only

- If the month and year of the incomplete stop date are the same as the month and year of the last study treatment, the day of the last study treatment will be assigned to the missing day
- If either the year of the incomplete stop date is before the year of the date of the last study treatment or if both years are the same, but the month of the incomplete stop date is before the month of the date of the last study treatment, the last day of the month will be assigned to the missing day
- If either the year of the incomplete stop date is after the year of the date of the last study treatment or if both years are the same, but the month of the incomplete stop date is after the month of the date of the last study treatment, the first day of the month will be assigned to the missing day

18.0 **CHANGES TO ANALYSES SPECIFIED IN PROTOCOL**

There is no change to the most recent protocol amendment (version 3.0), dated 20 Nov 2019.

19.0 **REFERENCES**

Not applicable.

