Prior medication is defined as any medication taken before the date of the first study treatment. *Concomitant medication* is defined as any medication taken on or after the date of the first study treatment. World Health Organization (WHO) Drug Dictionary, Global B3 version 201903 or newer, will be used to classify prior and concomitant medications by therapeutic class and drug name.

The number and percentage of participants with use of prior medications will be summarized by WHO drug class and preferred drug name for the Safety Population. Similarly, the number and percentage of participants with use of concomitant medications will be summarized by WHO drug class and preferred drug name for the Safety Population. If a participant took a specific medication multiple times or took multiple medications within a specific therapeutic class, that participant would be counted only once for the coded drug name or therapeutic class. Formulations (including salts, esters, etc.) containing the same active ingredient will be pooled under the coded drug name of the base compound. Medications containing multiple active ingredients of different coded drug names will be reviewed during the course of the study and may be pooled under a single coded drug name for analyses.

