- If the stop date is before the date of the first study treatment, the stop date will be assigned to the missing start date

17.8**MISSING DATE INFORMATION FOR PRIOR OR
CONCOMITANT MEDICATIONS**

For prior or concomitant medications, including rescue medications, incomplete (i.e., partly missing) start dates and/or stop dates will be imputed. When the start date and the stop date are both incomplete for a participant, the start date will be imputed first.

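### When two partial medication dates cross, SAP 17.8.1 and 17.8.2 correct them in opposite directions, and the start-first order makes one kind of drug with a pre-treatment stop month concomitant

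*SAP*

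**What the plan says.** SAP 17.8 fixes the order: "When the start date and the stop date are both incomplete for a participant, the start date will be imputed first".

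SAP 17.8.1 handles partial start dates. A start that gives only the year of first treatment takes the first-treatment date. The section then adds a correction for crossing dates. Its condition is "If the stop date is complete (or imputed) and the imputed start date is after the stop date", and its remedy is to give the start the stop date.

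SAP 17.8.2 handles partial stop dates. A stop whose month is known and earlier than the month of last treatment takes the last day of its recorded month. This section has its own crossing correction, worded to cover imputed as well as recorded starts: "If the imputed stop date is before the start date (imputed or non-imputed start date"), then "the imputed stop date will be equal to the start date".

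SAP 8.5 uses the resulting dates. A prior medication is one taken before the first-treatment date. A concomitant one "is defined as any medication taken on or after the date of the first study treatment".

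**The concern.** If both dates are imputed and the stop lands before the start, the conditions of both sections are met. One section pulls the start back and the other pushes the stop forward. SAP 17.8 does not say which correction takes precedence; the answer has to be inferred from the order of imputation.

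With the start imputed first, there is no imputed stop for 17.8.1 to compare it with. Its reference to an imputed stop therefore has no effect, and 17.8.2 makes the correction. That can carry a stop date out of its recorded month and onto the day of first treatment. The record then leaves the prior-medication table and enters the concomitant table, against what the site recorded. A programmer who took the 17.8.1 wording at face value would produce different tables from the same SAP.

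**Working it through.** The plan gives no figure to reproduce; the check is a trace of the date rules.

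**Inputs.** The rules are those of SAP 17.8, 17.8.1, 17.8.2 and 8.5. The calendar dates are assumptions for illustration: first treatment 15 Jun 2020, and last treatment either the same day (one session) or 10 Aug 2020 (two sessions, 56 days apart). The drug record is start 2020 (month and day missing) and stop Mar 2020 (day missing).

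| Step | Stated order, 17.8.2 corrects | 17.8.1 corrects |
|---|---|---|
| Impute start | 15 Jun 2020 | 15 Jun 2020 |
| Impute stop | 31 Mar 2020 | 31 Mar 2020 |
| Stop is before start | stop moves to 15 Jun 2020 | start moves to 31 Mar 2020 |
| Final dates | 15 Jun to 15 Jun 2020 | 31 Mar to 31 Mar 2020 |
| Class under SAP 8.5 | concomitant only | prior only |

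March precedes the month of last treatment in both cases, so one or two sessions give the same result. Stop May 2020 behaves in the same way: 15 Jun to 15 Jun 2020 (concomitant only) against 31 May to 31 May 2020 (prior only).

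**How far it reaches.** Other patterns with the same treatment dates:

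- Start 2020, complete stop 20 May 2020: 17.8.1 applies at once and the start becomes 20 May 2020. Prior, correctly.
- Start Apr 2020, stop May 2020: 30 Apr to 31 May 2020. No crossing; prior, correctly.
- Start 2019, stop May 2019: both dates become 31 Dec 2019. The stop leaves its recorded month, but the drug is still prior.
- Start 2020, stop 2020: concomitant under either rule, and here the recorded parts do not settle the timing.

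A wider enumeration took starts and stops on a 5-day grid from January 2019 to June 2020, with each date complete, day-missing, or month-and-day-missing (3 × 3 = 9 patterns). Only records whose recorded stop is certainly before first treatment were kept. In the stated order, a false concomitant class arose in one pattern: month-and-day-missing start with day-missing stop, in 496 of 5,460 grid records. All 496 had start and stop in the treatment year. The other eight patterns gave 0. With 17.8.1 making the correction, all nine gave 0.

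**The case against.** The strongest reply is that the algorithm is determinate. SAP 17.8 says "the start date will be imputed first", so 17.8.2 decides and there is no real contradiction. That much stands: read in order, the SAP gives one answer. But the answer is wrong for the pattern above, and the order leaves the imputed-stop wording of 17.8.1 with nothing to do, which invites the other reading.

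A second reply is that counting doubtful drugs as concomitant is a cautious convention. It is, where timing is doubtful. Here the recorded month settles the matter, and the drug also disappears from the prior table.

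A third reply is that few such records should remain, since Protocol 12.3 has missing or inconsistent data queried with the investigator. This is fair and supports treating the point as minor.

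A reader might also infer more than the documents support:

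- *Any drug stopped before treatment is at risk.* No. Both dates must be partial, in the one pattern described; complete stop dates are handled correctly.
- *The error feeds the concomitant-medication deviations of SAP 8.6.* That section says deviations are reviewed and documented before database lock. It does not derive them from imputed dates or from the medication tables. Blood thinners and diet pills, the obvious examples, are exclusion criteria 16 and 21 in Protocol 7.3.3, so they belong with eligibility deviations.
- *The 496 of 5,460 is an error rate.* It reflects the assumed dates and grid and says nothing about how often sites record dates this way.

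**Conclusion.** The point holds as a minor drafting fault with a definite wrong output. The two crossing corrections oppose each other, and in the stated order a drug with only the treatment year as its start and an earlier month of that year as its stop is moved onto the first-treatment date. Each such record is wrong twice: missing from the prior table and added to the concomitant table.

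The number of such records cannot be estimated from the documents. The visible text gives the classification no role in the CSQ primary analysis, the evaluable population or the classification of adverse events, so the effect is confined to the descriptive medication tables. The conclusion rests on a literal reading of the start-first order; the illustrative calendar dates do not drive it.

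**What to change.** State one precedence in SAP 17.8 and refer both subsections to it:

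- No imputed date may leave its recorded month or year.
- If the imputed start is after the imputed stop, set the start to the imputed stop where the recorded part of the start permits; otherwise set the stop to the start.

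Start 2020 with stop Mar 2020 then becomes 31 Mar to 31 Mar 2020, prior only. The second half of the rule is needed as well. Take start Sep 2020 and stop 2020, with last treatment on 10 Aug 2020. The imputed dates are 1 Sep and 10 Aug, the recorded September does not permit 10 Aug, and so the stop becomes 1 Sep, which agrees with both recorded parts. Restricting the 17.8.2 correction to complete starts would leave that record with its stop before its start. A complete start cannot move, so the 17.8.2 correction would continue to apply there. If the recorded parts themselves conflict (start Jun 2020, stop Mar 2020), no imputation satisfies both, and the record belongs in the query process of Protocol 12.3.

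The cost is one or two SAP sentences and a short code change. In the same edit, the reference in SAP 17.8.2 to Section 16.4 for a missing last-treatment date should point to 17.4, where that rule now stands.
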